6.3 Missing Data

Missing data will be minimised by careful data management. Missing data will be described with reasons given where available; the number and percentage of individuals in the missing category will be presented by treatment arm. No data will be considered spurious in the analysis since all data will be checked and cleaned before analysis.

Missing covariate data: If the amount of missing covariate data leads to exclusion of less than 5% of participants, and it is implausible that such exclusion is associated with outcomes or is not associated with observed outcomes, then missing data will be considered ignorable. Fully adjusted analyses will be based on all randomised participants using imputed covariate data using single conditional imputation. Sensitivity analyses will include adjusted analyses based on those with complete covariate profile.

If the amount of missing covariate data leads to exclusion of more than 5% of participants, and auxiliary variables can be identified that are associated with missingness with predictive value for the missing data, then multiple imputation will be employed, including observed outcomes, randomised treatment, auxiliary covariate data predictive of missingness and all variables which will be used in adjusted analyses. The imputation model will include all participants randomised in the group originally assigned.

Missing outcome data: The primary analysis method proposed is reasonably robust to missing at random (MAR) data conditional on all outcome measurements on all other visits and other covariates included in the model (**Table 1**). To address missing data, a multilevel mixed-effects model (cLDA) will be used, which implicitly accounts for intermittent missing data under the MAR assumption(Lu 2010).

Drop-out indicators will be created and we will report the counts of participants dropping out by arm, as well as the follow-up visit they dropped out of (**Table 3a**). For the purpose of our main analyses reporting outcomes up to 6 months, we consider a participant as having drop-out at a particular visit if all follow-up outcome assessments following that visit are all missing.

We will then examine any association of drop-out with important prognostic factors such as age, sex, education level, depression (PHQ-9), anxiety (GAD-7), and clinically significant SAEs relating to the interventions (Section 6.7), and baseline FIQR scores as well as follow-up FIQR scores observed before drop out.

6.4 Sensitivity Analysis

Complier Average Causal Effect (CACE): A sensitivity analysis will be undertaken to estimate the Complier Average Causal Effect (CACE), which aims to assess the treatment effect among participants who adhere to the assigned intervention(Peugh et al. 2017). CACE estimation accounts for non-compliance by using randomisation as an instrument to identify the causal effect of the treatment among those who would comply if assigned to the intervention.

A complier will be defined as a participant who completes at least 3 of the 6 digital CBT-I sessions, as session #3 contains sleep restriction therapy, thought to be the active component of CBT-I. A two-stage least squares (2SLS) instrumental variable (IV) approach will be employed to estimate the CACE, where randomisation is used as an instrument for treatment compliance. The first stage will model compliance as a function of treatment assignment and baseline covariates associated with compliance and the outcome. The second stage will estimate the effect of the treatment on FIQR, using predicted compliance as an instrumental variable. The exclusion restriction assumption assumes that randomisation only affects FIQR through treatment compliance.

Additionally, a continuous measure of compliance (0–6 sessions completed) will be used to estimate a doseresponse relationship between adherence and treatment effect. This will be explored using an instrumental variable approach or a generalised additive model (GAM) adjusting for baseline covariates to account for potential nonlinear associations. The relationship between compliance and outcome will also be visualised to assess potential threshold effects.

Balance in baseline characteristics between compliers and non-compliers will be examined. The robustness of CACE estimates will be explored by conducting sensitivity analyses, including alternative compliance definitions (e.g., different session thresholds) and addressing potential unmeasured confounding using a control function approach.

Informative drop out:

To assess the robustness of results to violations of MAR, Missing Not at Random (MNAR) scenarios will be explored using two complementary approaches:

1. Pattern-Mixture MNAR Model (δ -Based Imputation): A δ -adjusted imputation approach will be applied(Cro et al. 2020), where missing FIQR scores are adjusted by an offset δ , representing the assumption that missing data may be systematically worse (or better) than observed data. Sensitivity parameters will vary as follows:

- Optimistic scenario: δ =+1SD of observed FIQR.
- Neutral scenario: $\delta=0$ (equivalent to MAR).
- Pessimistic scenario: $\delta = -1$ SD of observed FIQR.

This approach will be implemented using the `rctmiss` command in Stata, ensuring that MNAR sensitivity analysis remains consistent with the primary model structure(White, Carpenter, and Horton 2018).

If treatment effects remain stable across MAR and MNAR analyses, findings will be considered robust. If treatment estimates shift significantly under MNAR models, this will indicate potential bias due to informative dropout.

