3.3 Sample Size

In the pilot phase (phase 1), the mean FIQR at baseline was 57.69 (SD=18.69). At the 3-month post-treatment follow-up, for the overall group, the mean FIQR was 52.24 (SD=19.06). The correlation between baseline and 3-month follow-up FIQR scores was high (r=0.86; 95%CI 0.73 to 0.93).

Using these values, the sample size was estimated to detect a minimum clinically-important difference (MCID) of 14% improvement in FIQR at 3 months (Bennett, Bushmakin, et al. 2009), corresponding to an improvement of 8.08 (Cohen's d=0.43) in this study, equating to a moderate effect size. Assuming a correlation of r=0.75 (the lower bound of the 95% CI for correlation), significance level of 0.05 and 80% power, the estimated sample size required to detect a 14% improvement in FIQR amongst participants in the Sleepio arm compared to the standard care arm using an ANCOVA is 78 participants (39 per group). This calculation includes an adjustment for a 3.33% loss-to-follow-up rate.

The R code used to estimate the sample size is provided below:

```

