3.7 Statistical Analysis Outline

It is anticipated that all the statistical analysis will be undertaken using R although other well-validated statistical packages, such as Stata, may be considered for statistical quality control validation analyses. All analyses will be carried out under a treatment policy strategy (that is, all participants will be analysed in the group they were randomised to regardless of actual treatment received).

The analyses will be repeated for the *per protocol* population (definition in section 4.2) as mandated by the protocol, bearing in mind that this may introduce bias by losing the benefits of randomisation and introducing ambiguity in the primary estimand of interest.

Although we have allowed for up to 5% missing data in the sample size at 3 months, we hope to minimise this by utilising data collection techniques appropriate to the fibromyalgia patient population. Before carrying out the within trial analysis, we will check the trial data for any missing data. Where possible the reasons for missing data will be ascertained and reported. The nature and pattern of the 'missingness' will be carefully considered — including whether data can be treated as missing at random (MAR). The handling missing data is detailed in section 6.3. Standard descriptive statistics will be used to describe the demographics between the treatment groups reporting means and standard deviations or medians and interquartile ranges as appropriate for continuous variables, and numbers and percentages for binary and categorical variables. All comparative outcomes will be presented as summary statistics and reported together with 95% confidence intervals and all tests will be carried out at a 5% two-sided significance level.

The Fibromyalgia Impact Questionnaire Revised (FIQR) at 3 months is the primary outcome of the study and the primary analysis will compare this between the treatment groups in a linear mixed effects method including all participant data, adjusting for the stratification factors.

Subgroups analyses will be undertaken with the aim of exploring the consistency of treatment effects across important baseline characteristics (Yusuf et al. 1991). These include:

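### SAP 6.4 reads the gap between the MAR and delta-adjusted estimates as a sign of informative drop-out, which it cannot be, and its robustness verdict is not tied to the primary 95% CI

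*SAP*

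**What the plan says.** SAP 6.4, under informative drop-out, announces two approaches to departures from MAR but lists only one. In that one, missing FIQR scores are shifted by an offset delta of +1 SD, 0 or -1 SD of observed FIQR. Two sentences then give the reading of the results. The first: "If treatment effects remain stable across MAR and MNAR analyses, findings will be considered robust". The second: "If treatment estimates shift significantly under MNAR models, this will indicate potential bias due to informative dropout".

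The section defines neither stability nor a significant shift, does not say in which arm or arms delta applies, and mentions neither the primary confidence interval nor the p-value. SAP 3.7 sets the standard for the trial's conclusions: "all tests will be carried out at a 5% two-sided significance level", with 95% confidence intervals.

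Two other places deal with drop-out. SAP 6.3 will examine its association with baseline factors and with FIQR scores seen before drop-out. Table 1 names a selection model that models drop-out jointly with the outcome; 6.4 does not carry it through.

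**The concern.** A delta analysis asks a what-if question: how would the answer change if the missing scores differed from the MAR prediction by this much? The analyst supplies the difference. Reading the resulting movement as a sign of informative drop-out turns an assumption into a finding. Unequal loss that was entirely random could be blamed on informative drop-out. Equal counts would give no shift under a common delta, whatever the mechanism.

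The verdict has a separate weakness. A reader wants to know whether the FIQR conclusion survives the SAP's own scenarios. The rule asks only whether the estimate stays stable, and leaves that word to be interpreted once the results are known. MAR is the main approach to missing data, and this section is the stated check on it, so the wording will shape how the primary result is reported.

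**Working it through.** **1. The SAP's sample size, to fix the inputs.** From SAP 3.3: baseline mean 57.69, SD 18.69, target difference 14%, r = 0.75, loss 3.3%, and "significance level of 0.05 and 80% power". The target is "corresponding to an improvement of 8.08 (Cohen's d=0.43) in this study".

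- Unadjusted n per arm: 2 × (1.96 + 0.842)² / 0.432² gives 85 after rounding up.
- Times (1 - 0.75²): 37.19.
- Divided by (1 - 0.033) and rounded up: 39 per arm, 78 in total. The SAP's figure reproduces.

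**2. What the shift is made of.** Let m1 and m0 be the numbers missing in the dCBT-I and control arms, and let delta be common to both.

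Shift = delta × (m1/39 - m0/39)

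At |delta| = 18.69:

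| Missing, dCBT-I v control | Shift (FIQR points) |
|---|---|
| 2 v 1 | 0.48 |
| 3 v 0 | 1.44 |
| 4 v 0 | 1.92 |
| 8 v 0 | 3.83 |
| any equal split | 0 |

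Using the 3-month SD of 19.06 instead raises these by about 2%.

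**3. Same counts, different mechanisms.** In 4,000 simulated trials per row (baseline-adjusted comparison, 39 per arm, true effect 8.08):

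| Missing | Drop-out | Mean shift | Bias of MAR estimate |
|---|---|---|---|
| 3 v 0 | random | 1.46 | 0.0 |
| 3 v 0 | worst outcomes leave | 1.44 | -1.9 |
| 8 v 0 | random | 3.91 | 0.1 |
| 8 v 0 | worst outcomes leave | 3.88 | -4.3 |

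The bias changes with the mechanism; the shift does not.

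**4. Shift against the primary conclusion.** SE = SD × √(1 - r²) × √(1/n1 + 1/n0). With 36 and 39 observed: 18.69 × 0.661 × 0.231 = 2.86.

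- Take an estimated benefit of 6.0 points and 3 v 0 missing. Under MAR, z = 6.0/2.86 = 2.10, p = 0.036. After the shift, (6.0 - 1.44)/2.86 = 1.60, p = 0.110. The estimate moved by only 0.50 SE, yet significance is lost.
- With SE about 2.85 at planned loss, a shift of 1.96 SE needs an excess of 1.96 × 2.85 / 18.69 × 39, or about 12 missing participants in one arm (30 percentage points). At the pilot correlation of 0.86 it needs about 9.

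**5. How often.** Simulation assumptions: 39 per arm, SD 19.06, r = 0.75, effect 8.08, common delta of ±1 SD, the same expected loss in each arm with counts varying by chance, and the MAR standard error kept after the shift. All three loss rates appear in the SAP: 3.33% in 3.3, 10% in a comment in its code, and 5% in 3.7 ("Although we have allowed for up to 5% missing data in the sample size at 3 months").

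| Loss per arm | Significance lost in some scenario | Shift above 1.96 SE |
|---|---|---|
| 3.3% | about 6% | 0.0% |
| 5% | about 8% | 0.0% |
| 10% | about 12% | 0.0% |

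With 4,000 trials per cell, the Monte Carlo standard error of the middle column is about 0.4 to 0.5 percentage points.

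**6. Marked imbalance, as an illustration.** At 30% v 10% loss, the shift exceeded 1.96 SE in about 7% of trials under random drop-out and 8 to 9% under informative drop-out. The MAR bias was about 0 in the first case and -3.2 points in the second.

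**The case against.** Several points on the other side stand.

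- **The SAP does not say that a result is robust when its conclusion flips.** A reader might infer this from 6.4, but stability is undefined, and an interval that moves across zero could fairly be called unstable. The text permits the bad verdict; it does not require it.
- **The alarm that is essentially never raised depends on one reading.** A reader might conclude that every trial would be declared robust. That follows only if a significant shift means more than 1.96 SE, a threshold that is assumed here and is not in the SAP.
- **Equal loss by the same mechanism in both arms leaves almost no bias in the treatment difference.** A verdict of robust there is not a missed detection. The fault in those cells is only the missing link to the conclusion.
- **Total changes of significance would overstate the harm.** They are about 11%, 14% and 20% at the three loss rates, but close to half are non-significant results becoming significant. Only losses are counted above.
- **The delta step is not the SAP's only look at drop-out.** The association checks in 6.3 and the selection model in Table 1 address mechanism, and 3.7 promises 95% confidence intervals, so a reader may be able to see an interval cross zero.
- **The 30% v 10% case lies far outside the planned loss** and serves only to show that the shift hardly separates the mechanisms.

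It can also be argued that the second sentence means only that the estimate would be biased if drop-out were informative. That would be a sound statement, but the text makes the shift the indicator. Neither 6.3 nor Table 1 corrects that sentence.

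**Conclusion.** The concern holds in two parts. First, the size of the delta shift carries no information about the drop-out mechanism. This is algebra and does not depend on how a significant shift is defined. Second, the robustness verdict is undefined and not tied to the primary 95% CI, so it allows a claim of robustness in the roughly 6%, 8% or 12% of trials (at 3.3%, 5% or 10% loss per arm) in which significance is lost under one of the SAP's own offsets.

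Those percentages rest on a common delta of ±1 SD, the SAP's ANCOVA planning inputs in place of the full cLDA model, a true effect equal to the target, and an unchanged standard error after the shift. The primary estimate and the sample size are not affected; what is at stake is the reported interpretation of the missing-data check.

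**What to change.** In SAP 6.4:

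1. Delete the sentence that takes a shift as indicating informative drop-out. Leave questions of mechanism to the association checks in 6.3 and the selection model in Table 1.
2. Report the 3-month FIQR difference and its 95% CI at each delta, and extend delta to the tipping point at which the interval first changes sides of zero. State the arm or arms to which delta applies: with a common delta and equal missing counts the shift is zero, and no tipping point need exist.
3. Call the primary result robust only if its conclusion is unchanged over the stated delta range. Otherwise report the tipping-point delta and say that the result depends on assumptions about the missing data.

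The new rule is not a test of mechanism either: at 30% v 10% loss, significance changed in about 65% of simulated trials under random and 36% under informative drop-out. It shows how far the conclusion depends on the assumption.

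The cost is a change of wording and a loop over delta in software already planned, with no new data. The downside is that some significant results will be reported as sensitive to missing data.

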6.5 Pre-specified Subgroup Analysis

We will investigate treatment effect modification by baseline sleep duration, an objective measure derived from actigraphy, to assess whether the effectiveness of digital CBT-I differs based on initial sleep duration. There is evidence suggesting that individuals with insomnia and objectively short sleep duration (<6 hours) may have distinct responses to cognitive-behavioural interventions compared to those with longer sleep durations(Vgontzas et al. 2013; Ballesio et al. 2019). This subgroup analysis aims to explore whether baseline total sleep time (TST) modifies the effect of digital CBT-I on the primary outcome (FIQR). None of the included subgroups are based on post-randomisation patient characteristics or events(Yusuf et al. 1991).

Participants will be categorised into two predefined subgroups:

- **Objective short sleep duration:** Baseline actigraphy-measured TST <6 hours
- Normal sleep duration: Baseline actigraphy-measured TST ≥6 hours

A treatment-by-subgroup interaction term will be included in the primary analysis model to formally test for effect modification. The interaction term will be as a continuous variable (TST as a linear predictor) to explore potential dose-response relationships.

To assess the consistency of effects across different levels of baseline sleep duration, estimated treatment differences will be summarised at the 25th, 50th, and 75th percentiles of the TST distribution. Results will be reported with estimated treatment effects and corresponding confidence intervals. Forest plots will be used to visualise subgroup effects.

Subgroup analyses will be conducted on the Analysis of Primary Estimand (ATE) (Treatment Policy Analysis) population. If there are fewer than 15 participants in any subgroup or fewer than 5 participants in one treatment arm within a subgroup, the analysis will not be conducted. Given the exploratory nature of this analysis results will be interpreted cautiously.

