Insomnia with objective short sleep duration: There is evidence that patients with insomnia with *objectively* short sleep duration (<6 hours) may respond differently to CBT-I(Vgontzas et al. 2013; Ballesio et al. 2019). For this subgroup analysis, an interaction between treatment allocation and baseline TST will be fitted to evaluate effect modification by sleep duration prior to randomisation. The continuous measure of TST will be used to maximise power.

Forest plots with 95% confidence interval will be used to present the subgroup analysis results.

Secondary clinical outcomes will be similarly analysed using mixed effects regression, using logistic regression for binary data and linear regression for continuous data. Any subsequent changes in this plan are strongly discouraged. If any changes to this SAP are implemented these will be documented in an updated version of this SAP. Documentation of any such changes will include the rationale for the changes, and when and by whom these were agreed.

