6.2 Analysis Methods

Analysis of Primary Estimand (ATE): A Treatment Policy Analysis

Unadjusted summary statistics of the FIQR scores will be displayed by treatment allocation using means and standard deviations at each assessment point. The primary analysis will be conducted using **Constrained Longitudinal Data Analysis (cLDA)**(Lu 2010). This model includes baseline FIQR as part of the response vector while constraining baseline means to be identical across treatment groups, ensuring that differences in FIQR post-randomisation reflect true treatment effects rather than baseline imbalance. This method offers advantages over traditional mixed-effects models (LMM) and ANCOVA by providing a more efficient and unbiased estimate of treatment effects while maintaining the interpretability of a baseline-adjusted analysis(Coffman, Edelman, and Woolson 2016; Lu 2010).

A linear mixed-effects model (LMM) with constraints will be used to compare FIQR scores between treatment groups across all available time points (baseline, 3-months, 6-months, and 12-months), ensuring that baseline differences are accounted for without requiring explicit adjustment in the fixed effects. The model will include a fixed effect for treatment group, time (categorical), and their interaction to allow for non-parallel treatment effects over time. To account for repeated measures within individuals, a random intercept will be specified for each participant, and an unstructured covariance structure will be assumed for residual errors to allow for flexible correlation between repeated measurements.

The constrained longitudinal model will be specified as:

$$Y_{i,t} = \mu + \gamma_t Time_t + \delta_t (Treatment_i \times Time_t) + \sum_k \beta_k Covariate_{k,i} + u_i + \varepsilon_{i,t}$$

where:

- *Y_{i,t}* is the FIQR score for participant *i* at time *t*
- μ is the grand mean FIQR score at baseline, constrained to be equal for both treatment groups
- $\gamma_t Time_t$ is the fixed effect of time (categorical), with baseline as the reference category
- δ_t is the interaction effect between treatment and time, estimating the treatment effect at each follow-up time point
- β_k represents covariate adjustment terms for stratification factors (sex, participation in the MRI substudy)
- $u_i \sim N(0, \sigma_u^2)$ represents the random intercept for participant i
- $\varepsilon_{i,t} \sim N(0, \sigma_t^2)$ is the residual error term

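### The sleep-duration subgroup term (SAP 6.5 and 3.7) has no time component; read literally in the constrained longitudinal model, it dilutes the 3-month interaction and costs the test most of its power

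*SAP*

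**What the plan says.** SAP 6.2 specifies a constrained longitudinal data analysis (cLDA). Baseline FIQR is part of the response vector, and the SAP describes the method as "constraining baseline means to be identical across treatment groups". In the printed equation, treatment enters only through its product with categorical time. The prose of 6.2 and Table 1 also list a fixed effect for treatment.

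On the subgroup, SAP 6.5 states: "A treatment-by-subgroup interaction term will be included in the primary analysis model to formally test for effect modification". It then makes the moderator continuous and asks for treatment differences at the 25th, 50th and 75th percentiles of TST, without naming a visit. SAP 3.7 says that "an interaction between treatment allocation and baseline TST will be fitted to evaluate effect modification by sleep duration prior to randomisation". Neither section mentions time, a TST main effect, TST x time, centring, or the 3-month contrast. SAP 6.5 calls the analysis exploratory and cancels it if a subgroup is too small.

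**The concern.** In an ANCOVA of 3-month FIQR, treatment x TST would be exactly the right term. In a cLDA it is not, because one of the outcome visits precedes treatment. A product term without time applies equally at every visit. It therefore releases the equal-baseline constraint along TST, and it estimates a single modification averaged over baseline, where the true value is zero, and follow-up. It also loses the within-person baseline adjustment that makes the 3-month contrast precise.

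At stake is the only pre-specified effect modifier. The percentile-specific effects and the forest plot would inherit a slope that is too shallow, and a null result could be misread as consistency of effect across sleep duration.

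**Working it through.** **Inputs from SAP 3.3 and 3.7.** "significance level of 0.05 and 80% power"; "all tests will be carried out at a 5% two-sided significance level"; baseline FIQR mean 57.69, SD 18.69; 14% target difference 8.08; baseline to 3-month correlation r = 0.75 (planning) and 0.86 (pilot); 3.3% loss to follow-up. Visits: four in SAP 6.2 (0, 3, 6, 12 months), three at the 6-month final analysis in SAP 3.5.

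**Assumptions not in the documents.** Correlations among the later visits, the course of the modification over time, and the mean and SD of TST.

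**The plan's own figure.** The SAP gives no power for the subgroup test. Its main sample size reproduces: d = 8.077/18.688 = 0.432; 2(1.960 + 0.842)²/0.432² rounds up to 85 per arm; 85 x (1 - 0.75²) = 37.19; 37.19/0.967 rounds up to 39 per arm, 78 in total.

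**Literal term.** Let V be the within-person correlation matrix over T visits and d = (0, 1, ..., 1) the pattern of a sustained modification. With centred TST and its main effect fitted, the expected generalised least squares coefficient, as a fraction of the true 3-month value, is 1'V⁻¹d / 1'V⁻¹1. Its relative variance is 1/(1'V⁻¹1).

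- Equal correlation: fraction (T - 1)/T, variance (1 + (T - 1)r)/T.
- AR(1) by visit order: fraction 1 - 1/(T - (T - 2)r), variance (1 + r)/(T - (T - 2)r).

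**Comparator.** The 3-month treatment x time x TST coefficient, with none at baseline, has fraction 1 and relative variance 1 - r².

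**Worked case (T = 3, r = 0.75, equal correlation).** Fraction 2/3. SE ratio √(0.833/0.4375) = 1.380. The z ratio is 0.667/1.380 = 0.483. A comparator with 80% power has expected z of 2.802, so the literal term has 0.483 x 2.802 = 1.353, and power is Φ(1.353 - 1.960) = 27%.

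| Correlation | r | Visits | Fraction kept | SE ratio | Power (comparator 80%) |
|---|---|---|---|---|---|
| Equal | 0.75 | 3 | 67% | 1.38 | 27% |
| Equal | 0.75 | 4 | 75% | 1.36 | 34% |
| Equal | 0.86 | 3 | 67% | 1.87 | 17% |
| Equal | 0.86 | 4 | 75% | 1.85 | 21% |
| AR(1) | 0.75 | 3 | 56% | 1.33 | 21% |
| AR(1) | 0.75 | 4 | 60% | 1.26 | 26% |
| AR(1) | 0.86 | 3 | 53% | 1.83 | 13% |
| AR(1) | 0.86 | 4 | 56% | 1.77 | 14% |

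At an assumed AR(1) r of 0.6 the fractions are 58% and 64%, so the full AR(1) range is 53-64%.

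**Size of modification behind the 80%.** With 75 evaluable participants the comparator's SE per SD of TST is √(4 x 18.69² x (1 - r²)/75), which is 2.85 at r = 0.75 and 2.20 at 0.86. Multiplied by 2.802, that is 8.0 and 6.2 FIQR points per SD of TST.

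**Simulation** (2,000 trials, N = 76, unstructured covariance, data generated with equal correlation, sustained modification). At r = 0.75 the literal term gave 0.66 of the truth and 28% power with three visits, and 0.75 and 34% with four. At r = 0.86 it gave 0.70 and 19%, and 0.78 and 23%. The 3-month three-way term was unbiased (1.00 to 1.02) with 76-78% power.

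**If modification is not sustained** (equal correlation). Fading as 1, 0.5, 0.25 over four visits leaves 44% and 10-15% power. Present at 3 months only, it leaves 25-33% and 7-10%.

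**Raw hours.** If TST is uncentred and, as in the printed equation, no treatment main effect is fitted, the term forces a mean baseline arm difference of coefficient x mean TST, which the baseline data pull towards zero. With assumed mean 6.3 h, three visits, r = 0.75 and equal correlation, the fraction kept is 1.0%, 2.0% and 4.2% for SD 0.7, 1 and 1.5 h. With a treatment main effect, raw hours returns the same 67% and 75% as centred TST.

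**The case against.** The best defence is that the SAP never says the interaction is two-way. In the equation the treatment effect exists only as treatment x time, and the primary outcome is FIQR at 3 months, so an analyst could fit treatment x time x TST without contradicting 6.5 or 3.7. That stands. A reader might infer that the plan commits the trial to a wrong estimate. The text does not support this; it shows that the time component is unstated and that the literal reading is a poor one.

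A reader might also infer that real effect modification would all but vanish from the estimate. That needs raw-hours TST and no treatment main effect together, whereas the prose of 6.2 and Table 1 include that main effect. Otherwise, for a sustained modification with three or four visits, the estimate is diluted to between about half and three-quarters. The heavy loss is in the power of the test.

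Finally, the analysis is exploratory, to be read cautiously, and leaves the primary comparison untouched. That limits the consequence. It does not excuse leaving open a choice that decides what the sole pre-specified subgroup test estimates.

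**Conclusion.** The point holds as a specification defect with a measurable cost. Taken literally, the stated term acts at baseline and recovers about 67% (three visits) or 75% (four) of a sustained modification under equal correlation, and 53-64% under AR(1) with r of 0.6-0.86. Power that would be 80% for the 3-month three-way term becomes about 17-34% under equal correlation and 13-26% under AR(1), for r = 0.75-0.86. That the coefficient is diluted follows from the model and needs no outside figure. The exact sizes rest on the assumed later-visit correlations and on modification being sustained; if it fades, the loss is greater. The figure of about 2% applies only to the raw-hours, no-main-effect case, with TST mean and SD assumed.

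**What to change.** In SAP 6.5, and in matching words in 3.7:

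- Centre baseline TST.
- Add to the primary model TST, TST x time, and treatment x time x TST at the follow-up visits only, with no treatment x TST term at baseline.
- Name the 3-month three-way coefficient as the test of effect modification.
- Take the treatment effects at the 25th, 50th and 75th TST percentiles, and the forest plot, from the 3-month visit.

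It would also help to reconcile the prose of 6.2 and Table 1 with the equation on whether a treatment main effect is fitted, since that main effect would itself release the baseline constraint.

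The cost is a wording change and a few extra parameters (two per follow-up visit plus the TST main effect). No new data are needed.
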